2. OBJECTIVES

Primary objective:

- To compare the incidence of central line-associated bloodstream infection (CLABSI) rate in patients using antimicrobial-impregnated central venous catheter (CVCs) and non-impregnated CVCs in Malaysia adult Intensive Care Unit (ICU)

Secondary objectives:

- To determine the length of stay of patients using antimicrobial-impregnated central venous catheter (CVCs) vs non-impregnated CVCs in Malaysia adult Intensive Care Unit (ICU)
- To undertake a cost-effectiveness analysis in prevention of central line-associated bloodstream infection (CLABSI) between patients using antimicrobial-impregnated central venous catheters (CVCs) and non-impregnated CVCs in Malaysia adult Intensive Care Unit (ICU)
- To compare the antimicrobial resistance features of the bacterial species that caused central line-associated bloodstream infection (CLABSI) between patients using antimicrobial-impregnated central venous catheter (CVCs) and that of non-impregnated CVCs in Malaysia adult Intensive Care Unit (ICU)

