3.6 Sample Size

Our local data at ICU, UMMC reported the incidence of CLABSI per 1000 catheter days in the first 6 months of 2022, to be 12.18. Using SAS® for sample size calculation, in order to detect a clinically significant reduction of CLABSI by 30%, and assuming a two-sided type I error protection of 0.05 and a power of 0.80, we calculated a sample size of 50 patients is required. To incorporate a 10% drop out rate, we therefore aim to recruit 55 patients in each arm (antimicrobial-impregnated CVCs, n=55; non-impregnated CVCs, n=55). This will make up to a total sample size of 110.

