3.7.2 Other Parameters

Baseline patient data will be included as concomitant study parameters. Relevant patient and clinical data including basic demographic information (age, gender, and ethnicity), known underlying diseases, previous antibiotic exposure within 90 days, and admission date will be extracted from the clinical database for correlation and risk factor analyses.

For patients diagnosed with CLABSI, information including the number of days a patient spent in the hospital prior to strain isolation, number of days and type(s) of antibiotics used in said patient, hospital-generated antibiograms for each strain, patient risk factors for nosocomial infection associated with an isolate, previous surgeries or hospitalizations of the patient prior to isolation, location of a patient within the hospital prior to strain isolation and ICU admission, and any other information pertinent to a specific strain that will not identify a patient will be collected.

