3.9 Data Analysis

The data will be analysed using the SPSS Software. Descriptive statistics will be expressed as percentages unless otherwise stated. Categorical variables will be expressed as percentages and compared using the Chi-square or Fisher's exact test, whichever is appropriate. Variables with a univariate test value of less than 0.05 (p-value) will be included in a multivariate analysis using a logistic regression model. Odds ratios (OR) and 95% confidence intervals (CI) will be calculated to identify the risk factors associated with the development of CLABSI in patients. In all instances, a p-value of less than or equal to 0.05 will be considered significant.

FUNDING

This study will be funded by Teleflex Research Grant (RM50000).

RESEARCH DATA MANAGEMENT

All data collected will be handled confidentially according to the Good Clinical Practice Guidelines. The paper case report forms will be stored within a locked cabinet at the Department of Anaesthesiology, Faculty of Medicine, Universiti Malaya. The electronic case report forms will be kept in a password-protected laptop. Only the study investigators will have access to the research data. The data will be kept for seven years upon completion of study. The results of the study will be reported in a thesis. The results will also be presented in conferences and published in scientific journals.

POTENTIAL RESEARCH IMPACT

The usage of antimicrobial-impregnated central venous catheters (CVCs) among adult critically ill patient in the Intensive Care Unit (ICU) can reduce central line-associated bloodstream infections (CLABSIs) and this will translate to reduced patients' length of stay and healthcare costs.

GANTT CHART

	2023												2024											
Research Activities	3	4	5	6	7	8	9	10	11	12	1	2	3	4	5	6	7	8	9	10	11	12		
Ethics submission	█	█																						
Patient recruitment			█	█	█	█	█	█	█	█	█	█	█	█										
Data collection			█	█	█	█	█	█	█	█	█	█	█	█										
Data analysis															█	█	█							
Completion and submission of manuscript																		█	█	█				
Publication and scientific presentations																					█	█		

REFERENCES

- Alotaibi, N. H., Barri, A., & Elahi, M. A. (2020). Length of Stay in Patients With Central Line-Associated Bloodstream Infection at a Tertiary Hospital in the Kingdom of Saudi Arabia. *Cureus, 12*(10). <https://doi.org/10.7759/CUREUS.10820>

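### Screening on univariate p<0.05 makes the risk-factor odds ratios that enter the plan's only multivariable model, on average, too far from 1

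*Combined protocol and SAP*

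**What the plan says.** Section 3.9 compares categorical variables between groups, "compared using the Chi-square or Fisher's exact test, whichever is appropriate". It then sets the entry rule for the multivariable analysis: "Variables with a univariate test value of less than 0.05 (p-value) will be included in a multivariate analysis using a logistic regression model". ORs with 95% confidence intervals "will be calculated to identify the risk factors associated with the development of CLABSI in patients".

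The candidates come from section 3.7.2: "basic demographic information (age, gender, and ethnicity), known underlying diseases", then "previous antibiotic exposure within 90 days, and admission date will be extracted from the clinical database for correlation and risk factor analyses". That is at least six variables, and more if underlying diseases are split.

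This is the only multivariable model in the document. There is no prespecified covariate set, penalisation, validation sample or other allowance for selection. The analysis is not labelled exploratory.

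The objectives in section 2 do not mention risk factors. The primary one reads "To compare the incidence of central line-associated bloodstream infection (CLABSI) rate in patients using antimicrobial-impregnated central venous catheter (CVCs) and non-impregnated CVCs".

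**The concern.** A variable reaches the model only if its observed association is strong enough for p<0.05 in this sample. When events are few, that threshold lies far from 1. A factor with a modest true effect can therefore enter only when chance has enlarged its estimate, and its OR is then computed from the same enlarged data. Its confidence interval takes no account of this.

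What is at stake is how strong the published risk factors look. For modest true effects, the intervals would also miss the truth more often than their 95% label says.

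**Working it through.** The plan gives no figure for this analysis, so there is none to reproduce.

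**Inputs from the documents (section 3.6).** The unit "reported the incidence of CLABSI per 1000 catheter days in the first 6 months of 2022, to be 12.18"; the target is a 30% reduction; and "we calculated a sample size of 50 patients is required", read as per arm because 55 per arm follows after 10% dropout.

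**Assumed, because the documents do not say.** Mean catheter days d from 5 to 21; candidate prevalence 30 to 50% (40% in the simulations); true ORs of 1.5, 2 and 3; six independent binary candidates.

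**Step 1: expected events.** Risk per patient = 1 − exp(−rate × d), with rates 0.01218 and 0.7 × 0.01218 = 0.008526. At 10 days: 50 × (0.1147 + 0.0817) = 9.8. At 5, 7 and 21 days: 5.0, 7.0 and 19.5. With six candidates this is 0.8 to 3.2 events per candidate.

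**Step 2: smallest OR above 1 that can pass.** Take 100 patients, 40 with the factor.
- 19 events: the first passing split is 12/40 v 7/60, OR = (12 × 53)/(28 × 7) = 3.24.
- 10 events: the first passing split is 8/40 v 2/60, OR = (8 × 58)/(32 × 2) = 7.25.

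Across 30 to 50% prevalence, using Fisher throughout or chi-square where the smallest expected count is at least 5, the thresholds are 3.2 to 3.5 (19 events) and 4.6 to 10.8 (10 events). A crude OR near 1.5 or 2 cannot pass.

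**Step 3: hand approximation.** With 110 patients, 11 events and 40% prevalence, SE(log OR) = 1/√(110 × 0.4 × 0.6 × 0.1 × 0.9) = 0.649, so the threshold is exp(1.96 × 0.649) = 3.57. For a true OR of 1.5, t = 0.405/0.649 = 0.625.
- Chance of passing: P = 1 − Φ(1.96 − t) + Φ(−1.96 − t) = 0.096.
- Mean z given passing: t + [φ(1.96 − t) − φ(1.96 + t)]/P = 2.185.
- Mean OR given passing: exp(2.185 × 0.649) = 4.1.

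True ORs of 2 and 3 pass 19% and 40% of the time and then average 5.0 and 5.6.

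**Step 4: simulation of the stated procedure.** 50 per arm; arm plus six binary candidates, two with the stated true OR and four null. Screen at p<0.05, fit logistic regression on all entrants, 40,000 trials per setting. The average is the geometric mean OR of entrants with a true effect; coverage is for the Wald 95% interval. Ranges span the two test rules.

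| True OR | Days | Average OR of entrants | Coverage |
|---|---|---|---|
| 1.5 | 10 | 5.5 to 5.8 | 78 to 79% |
| 1.5 | 21 | 3.4 to 3.7 | 76 to 80% |
| 2.0 | 10 | 6.2 to 6.5 | 93% |
| 2.0 | 21 | 3.9 to 4.1 | 91 to 92% |

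A true OR of 1.5 enters in 7.0 to 7.5% of trials at 10 days and 10.2 to 13.1% at 21 days. Smaller repeat runs with the Fisher rule agree within simulation error: averages about 5.9 and 3.7, coverage down to 75% at 21 days. At a true OR of 3, coverage is 99% (10 days) and 96% (21 days). Entries with no finite maximum-likelihood estimate were excluded: 10 to 11% at 10 days, at most 0.2% at 21 days. Below 10 days no average is given, because 31 to 57% of entries have no finite estimate.

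**Step 5: is it the screen?** In a separate simulation with 110 patients, eight candidates and 11 events, true ORs of 1.5, 2 and 3 averaged 1.59, 2.25 and 3.59 with every candidate fitted, and 4.72, 5.83 and 6.52 after the screen. Most of the excess therefore comes from selection and a small part from ordinary small-sample bias. With predictors correlated at 0.3, the screened averages for true ORs of 2 and 3 fell from 5.8 and 6.5 to 4.3 and 5.4.

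**Step 6: what prespecification buys.** Arm plus two named covariates, Firth fit, true OR 1.5. Reported in full, the covariates average 1.5 with 96 to 97% coverage. Looking only at those with p<0.05, they average 5.4 at 10 days (coverage 80%) and 3.5 at 21 days (82%).

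**The case against.** The strongest objection is that a screened average is conditional on significance, while a prespecified average is not, so setting one against the other flatters the fix. That stands. Step 6 shows almost the same exaggeration once attention is limited to significant covariates. A reader might infer that naming covariates in advance removes the bias; it does so only when every named covariate is reported.

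The root cause is the shortage of events. That also stands. With about 100 events among 1000 patients, the excess nearly vanishes for true ORs of 2 or more. But the shortage is a matter for section 3.6, and the screen adds an avoidable distortion to it.

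The harm is infrequent at a modest effect. At a true OR of 1.5, nothing enters the model in 73% (10 days) and 64% (21 days) of simulated trials. This limits how often the problem arises, but not its size when it does.

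Section 3.9 does not say that ORs will be given only for variables that pass the screen. True; the point therefore concerns the ORs that reach the model.

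A reader might also infer that the catheter comparison is biased. The documents do not support this: they promise no adjusted catheter effect, section 3.7.2 does not list arm among the risk-factor variables, and the unadjusted randomised comparison does not pass through the screen.

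**Conclusion.** The concern holds for the exploratory risk-factor analysis. The direction, on average too far from 1, appeared in every trial-sized setting examined. It describes an average: a single OR may still move towards 1 or change sign when a correlated factor is left out.

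The sizes depend on assumed catheter days, prevalence, true ORs and independent binary candidates. Age, ethnicity and admission date are not naturally binary, and correlation reduced the averages. It would be too strong to say that the intervals fail generally, since under-coverage is mainly a problem for modest effects. No objective in section 2 depends on this model, so the change is worthwhile but optional.

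**What to change.** In section 3.9:

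1. Replace the p<0.05 screen with a short covariate list drawn from section 3.7.2, named before outcome data are seen and sized to the expected number of CLABSIs.
2. Report the OR and 95% interval of every listed covariate whatever its p-value, and do not single out the significant ones as identified risk factors.
3. Label these ORs exploratory.

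A sparse-data fit such as Firth is a useful addition but does not replace step 1: with the screen kept, a true OR of 1.5 still averages 4.8 to 4.9 (10 days) and 3.3 to 3.5 (21 days) under Firth. As a minor wording point, if arm is put in a multivariable model, keep it there whatever its univariate p-value.

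The cost is analysis wording, plus a check that the SPSS version in use offers Firth if it is chosen. The downside is that fewer risk factors can be claimed. The shortage of events remains.
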